6.3 Tertiary endpoint(s)

Our study, in line with current recommended practice (HIQA guideline, see references), proposes to examine the DI cost-effectiveness from the wider public health services perspective including possible costs and benefits accrued via the community services and rehospitalizations. The study aims to assess

the following cost-effectiveness measures of the DI as delivered by a trained physician and by a trained pharmacist:

- (i) Quality Life Adjusted Year (QALY),
- (ii) cost per hospital readmission avoided, and
- (iii) cost per ED attendance avoided.

For the economic analysis, all ED attendances and all unscheduled readmissions of all randomized patients will be taken into account, as well as the quality-of-life status of all followed up randomized patients (EQ5D-5L; see Appendix 1).

6.3 Safety outcomes (if relevant)

FORTA criteria (Kuhn-Thiel et al.) will be applied at baseline, at discharge, at day 30 and at day 180. FORTA criteria are validated explicit indicators of medication appropriateness. FORTA criteria category D in particular identify those medications that should be avoided in individual cases. Other FORTA labels range from A (indispensable) to B (beneficial), to C (questionable). FORTA criteria will provide an objective measure of medication safety in OPTIMATE. Patients in the 3 arms of the trial will be compared in terms of proportions with FORTA category A, B, C and D medications as indicators appropriateness/inappropriateness of medication.

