3.3 Safety Objectives (if applicable)

- To minimize the prevalence of medications to be avoided in multimorbid older people.

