4.2.1 Subjects Eligibility Criteria

Inclusion criteria:

- I. Age \geq 70 years (male or female).
- II. \geq 3 chronic medical conditions.
- III. \geq 5 daily medications pre-admission, all medications taken for at least 4 weeks continuously.
- IV. Can speak and understand English (in the two Irish medical centres), and Dutch or French in Ghent University Hospital (Ghent is predominantly Dutch-speaking).
- V. Can give written informed consent, or give witnessed verbal consent or have a suitable proxy who can give informed assent on the patient's behalf.
- VI. Agrees to follow-up contact post-discharge up to 180 days post-discharge.
- VII. Agrees to primary researcher contacting the GP and community pharmacist post-discharge.

Exclusion criteria

- I. Terminal illness.
- II. Severe dementia and clearly unable to understand the purpose of the trial or give consent to participation.
- III. Severe communication disorder, making informed consent impossible.
- IV. Likely to be discharged from hospital within 48 hours of arrival.
- V. ICU admission.
- VI. Primary psychiatric presenting illness.
- VII. Unavailable for post-discharge follow-up for any reason.
- VIII. Non-accidental poisoning.
- IX. Previous participation in medication optimization trials.
- X. Participation in another clinical trial.
- XI. Infectious illness requiring strict isolation (including COVID-19 infection) blocking access of the primary researcher to the patient for enrolment.
- XII. End-stage renal, liver or lung disease requiring organ replacement therapy.
- XIII. Admitted under the care of specialists in Clinical Pharmacology, Palliative Medicine, Clinical Oncology or Haematology.
- XIV. Admitted under the care of specialists in Geriatric Medicine in Ghent University Hospital.
- XV. Trial participation refusal.

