7.2. Statistical Analysis

Treatment effects for each of the two active intervention arms (versus control) in terms of binary outcomes (e.g. readmission) will be estimated using logistic regression, while Health Related QoL (EQ-5D 5L) will be analyzed using ordinal regression with a logit link function (i.e. a proportional odds model). We will report two models for each outcome: one adjusted for centre and admitting service type; and another further adjusted for age (years), sex, number of comorbidities at baseline, and number of prescribed medications at baseline. Effect estimates will be reported as odds-ratios with 95% confidence intervals and exact p-values. There will be no correction for multiplicity, but we will report results for all outcomes regardless of the result and provide enough information for the reader to make whatever corrections they may consider appropriate. Equivalence tests comparing the two active arms (for each outcome) will be done using a “two one-sided tests” procedure based on a 90% confidence interval (which equates to a 5% type 1 error rate). All analyses will be conducted on an intention-to-treat basis and will be conducted under the quality system and SOPs of the HRB CRF-C Statistics and Data Analysis Unit. A complete statistical analysis plan (SAP) will be pre-registered on the Open Science Framework prior to database lock. Any necessary deviations from this SAP will be documented and explained in the trial report. There will be only one single trial data analysis at the end of the project. All reporting will be carried out in accordance with CONSORT guidelines for clinical trials.

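### FORTA, the only listed safety outcome, is scored at baseline in every arm, but no stated analysis uses that value and category D is not named as the main measure

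*Combined protocol and SAP*

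**What the plan says.** Section 6.3 (Safety outcomes) contains one measure, FORTA. Mortality is a secondary outcome (section 6.2), and section 11.1 is a reporting procedure for events arising from the intervention.

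The criteria "will be applied at baseline, at discharge, at day 30 and at day 180", and Tables 1a and 1b schedule them for intervention and control patients alike. The comparison is one sentence, whose subject is the patients of the three arms: they are to be "compared in terms of proportions with FORTA category A, B, C and D medications". The same section says that "FORTA criteria category D in particular identify those medications that should be avoided in individual cases". Section 3.3 gives a single safety objective: "To minimize the prevalence of medications to be avoided in multimorbid older people".

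Section 7.2 sets out two models per outcome. One adjusts for centre and admitting service type. The other is "another further adjusted for age (years), sex, number of comorbidities at baseline, and number of prescribed medications at baseline". Section 7.2 does not mention FORTA by name, and baseline FORTA is in neither list. A complete SAP is to be registered before database lock.

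**The concern.** Three things are left open for the only safety outcome.

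- **Baseline.** Drugs brought into hospital will largely determine the drugs seen later. A patient's own baseline D value is therefore likely to be the strongest predictor of the follow-up value. It is collected in every arm and not put to use.
- **Main measure.** Four categories, three post-baseline times and two active arms against control give 4 × 3 × 2 = 24 comparisons. Section 7.2 applies no multiplicity correction. Nothing says that D is the one to read, although the objective points to it.
- **Unit.** The sentence can mean the share of patients with at least one drug in a category, or the share of drugs in that category. The two can give different answers.

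At stake are the precision and clarity of the safety result. The readmission and emergency attendance results do not depend on it.

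**Working it through.** The documents give no FORTA frequencies and no baseline-to-follow-up correlation. Every FORTA rate below is an assumption.

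**1. Patients available.** Section 4.3 plans 324 evaluable patients per arm for 20% against 12%, at 5% two-sided and 80% power.
- Pooled formula: n = [1.96√(2 × 0.16 × 0.84) + 0.8416√(0.20 × 0.80 + 0.12 × 0.88)]² / 0.08² = 329. The unpooled form gives 326.
- Both are close to 324, where power is 79.5%. Then 972 / 0.7 = 1389, as stated.
- I use 324 per arm below.

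**2. Value of the baseline score.** For a count or continuous score in a linear model, adjustment leaves a fraction 1 − ρ² of the variance, so 324 patients act like 324 / (1 − ρ²).
- ρ = 0.3: 91% left, 9% removed, acts like 356.
- ρ = 0.5: 75% left, 25% removed, acts like 432.
- ρ = 0.7: 51% left, 49% removed, acts like 635.

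This is the gain over a model with no related covariate. It does not transfer directly to a yes/no outcome in logistic regression.

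**3. Any D drug as a yes/no outcome, unadjusted.** If 30% to 50% of control patients have a D drug, 80% power at 324 per arm needs a fall of 9.5 to 10.9 percentage points.

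**4. Partial stopping on the patient-share reading.** Section 2.1 reports implementation of STOPP advice of 39.2% (pharmacist) and 81.2% (physician) in two earlier trials. Assume that these rates apply independently to each drug of a patient with two D drugs.
- At 39.2%: at least one stopped, 1 − 0.608² = 63%; both stopped, 0.392² = 15%. So (63 − 15) / 63, about three-quarters of improved patients, still count as having a D drug.
- At 81.2%: at least one stopped, 1 − 0.188² = 96%; both stopped, 0.812² = 66%. About one-third of improved patients still count.

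**5. Simulation.** There were 500 runs per scenario and four scenarios, with 324 per arm. The chance of keeping each D drug was 10 points lower with the intervention (0.8 to 0.7, or 0.7 to 0.6). Mean baseline D count was 0.6 to 2.0, overdispersed, with a mean of 0.1 to 0.3 new D drugs. Control prevalence of any D was 41% to 74%.
- Any D, unadjusted: power 11% to 18%.
- Any D, adjusted for baseline any D: 18% to 28%.
- D count, adjusted for baseline D count: 41% to 81%.

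The simulated correlation was 0.82 to 0.89, above the range in step 2, and no other covariates were modelled, so these gains are at the favourable end. The last line changes both the measure and the covariate and does not separate the two effects.

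**6. Is there a ceiling for category A?** The chance of at least one A drug among k independent drugs is 1 − (1 − q)^k, where q is the share of drugs in A. Entry requires at least "5 daily medications pre-admission, all medications taken for at least 4 weeks continuously".
- k = 5: 83% if q = 0.30, but 67% if q = 0.20.
- k = 8: 94% if q = 0.30, and 83% if q = 0.20.

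The result depends on q, which the documents do not give.

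**7. Share-of-drugs reading.** Categories are then exclusive, and the points in steps 4 and 6 fall away. The denominator, however, moves with every drug started or stopped. Since START prompts additions, the D share could fall with no D drug removed. The unused baseline remains an issue on this reading too.

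**The case against.** The strongest case against is that much of this is silence. Section 6.3 does not limit the comparison to follow-up values, section 7.2 does not mention FORTA by name, and a full SAP is still to come. That stands as far as it goes: baseline use is unstated, not ruled out. But section 7.2 gives fixed covariate lists for each outcome, and baseline FORTA is in neither, so an analyst following the text would leave it out.

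The share of patients with a D drug is also a legitimate reading of prevalence in section 3.3. That stands, so a count is a preference, made for sensitivity, and not a correction of an error.

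The second model already adjusts for number of medications, which may absorb part of the gain. That stands, although total drugs is not the D count and the first model has neither.

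A reader might infer more than the documents support:
- **That overlapping categories are an error.** Four separately reported proportions may overlap, and nothing treats them as exclusive.
- **That the category A proportion sits near its ceiling.** This is possible, but it needs the patient-share reading and an assumed A share.
- **That the comparison is biased.** Chance baseline differences under stratified randomization cost precision and do not bias the estimate.

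**Conclusion.** The point holds as one of lost precision and unclear definition in the only listed safety outcome. On any reading, the baseline value is collected and not used in the stated analysis, and category D, the one that matches the objective, has no priority over A, B and C. On the patient-share reading, partial stopping of D drugs is also missed.

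The size is conditional. For a count or continuous score, assumed correlations of 0.3 to 0.7 remove about 9% to 49% of the variance, and less when number of medications is in the model. Under the simulated rates, baseline adjustment raised power for any D from 11–18% to 18–28%, and a baseline-adjusted D count reached 41–81%. These are illustrations, not forecasts for this trial.

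It is worth changing before the SAP is registered. FORTA carries no sample size and no decision rule, so the primary conclusions do not depend on it.

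**What to change.** In section 6.3 and the SAP:

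- Define the unit, and name category D as the main FORTA measure.
- Analyse it at discharge, day 30 and the last visit, with the patient's own baseline category D value as a covariate in addition to centre and admitting service type. The second model can keep its further covariates.
- Preferably use the number of D drugs per patient, in a count model or in the proportional-odds model that section 7.2 already uses for quality of life, with the baseline count as covariate.
- Show the proportion of patients with any D drug, and the A, B and C results, as supporting or descriptive.

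Naming D as the main measure cuts the main comparisons against control from 24 to 1 × 3 × 2 = 6.

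The cost is SAP wording and a short protocol clarification; all the data are already scheduled in every arm. The downside is that a count is slightly less simple to present than a percentage, which can still be reported beside it.

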7.0 Data Management and Statistical Analysis

7.1. Data Management

The research team will engage closely with HRB data stewards based in the Statistics and Data Analysis Unit (SDAU) of the UCC HRB CRF-C. Before study initiation, study staff will be instructed by members of the SDAU on data collection, organization and eCRF entry techniques that adhere to the FAIR data principles and will guide development of the study data management plan.

The data obtained in OPTIMATE will include details of patients' age, sex, physical function, cognitive function, clinical diagnoses, medications, drug doses, laboratory test results indicating kidney and liver function, quality of life and survival at follow-up. Overall, the study will enroll approximately 1400 patients across three participating medical centres. The entire data collection is not expected to exceed 100 GB of digital storage.

Data collection will be performed using a third-party electronic data capture (EDC) system ensuring consistent data entry, documentation and security between research sites. Where applicable, variable data measurements will be recorded using international standardized units. All variables are to be recorded within Comma Separated Value (.csv) data tables. Data files will include metadata identifying title, creator, keywords etc. in line with the Dublin Core Metadata Initiative alongside accompanying data dictionaries which will be developed in parallel. Medical coding of adverse events (MedRA) and medications (WHODrug) will be enacted as part of the EDC platform. Throughout the OPTIMATE study, routine data visualization and exploration approaches using the R statistical computing and graphics language will be performed. This will allow for the development of standardized documentation of both data review and reporting processes, in collaboration with the SDAU, that is both reproducible and linked to version control strategies.

Data storage and back-up will be dictated by the EDC supplier allowing for two-factor authentication and establishment of defined user access permissions and audit trails. All OPTIMATE trial data will be collected electronically and entered on a bespoke trial proforma. Once verified as

fully correct and complete, all individual participant trial data will be stored on a fully secure clinical trial database, the Castor electronic data capture system (Castor EDC) on the server located in the Netherlands. The Castor EDC system is compliant with ICH E6 GCP, GDPR, ISO 27001 and ISO 9001 standards and regulations. Pre-existing UCC IT research infrastructure protocols will provide for secondary backups of the OPTIMATE trial data. All personally identifiable data relating to participating patients is subject to General Data Protection Regulation (GDPR) and the Irish Health Research Regulations. Accordingly, all staff with data access permissions will be required to undergo training in GDPR to ensure that all data collected for the purposes of the OPTIMATE trial will be treated with the highest standards of security and confidentiality. Ethical approval for this study was granted by the Clinical Research Ethics Committee of the Cork Teaching Hospitals , HSE South Eastern Area Research Ethics Committee for the University Hospital Waterford Centre and from the : Commissie voor Medische Ethisiek van het UZ Gent/Committee on Medical Ethics Ghent University Hospital for Ghent University & Ghent University Hospital. This study will also follow the guidelines set out by the UCC code of Research Conduct and Research Integrity.

Participation in the OPTIMATE trial and the identity of the subjects, both those screened and those enrolled and randomized, will be treated as confidential and no participant identifiable records or results relating to the study will be disclosed to any third party other than the authorized investigators. Personal identifiers will undergo pseudonymization. An encryption key, held securely away from the data, will be accessible to the project Principle Investigator at the coordinating site only.

Consent from patients participating in OPTIMATE will be obtained for all data to be shared publicly, such as data used in the generation of publications arising from the study, and in accordance with CRF-C Standard Operating Procedures. Data sharing repositories will be formerly identified via careful alignment of the expected data object outputs and evaluated using the re3data resource (re3data.org). This is to ensure maximum utility and interoperability of the final data package(s) and assignment of a persistent digital object identifier (DOI). Additional post-study data provenance will be enacted through sharing of analysis scripts and study protocols via Open Science Framework projects with an accompanying DOI(s) and/or through the HRB Open Research publishing platform.

7.2. Statistical Analysis

Treatment effects for each of the two active intervention arms (versus control) in terms of binary outcomes (e.g. readmission) will be estimated using logistic regression, while Health Related QoL (EQ-5D 5L) will be analyzed using ordinal regression with a logit link function (i.e. a proportional odds model). We will report two models for each outcome: one adjusted for centre and admitting service type; and another further adjusted for age (years), sex, number of comorbidities at baseline, and number of prescribed medications at baseline. Effect estimates will be reported as odds-ratios with 95% confidence intervals and exact p-values. There will be no correction for multiplicity, but we will report results for all outcomes regardless of the result and provide enough information for the reader to make whatever corrections they may consider appropriate. Equivalence tests comparing the two active arms (for each outcome) will be done using a “two one-sided tests” procedure based on a 90% confidence interval (which equates to a 5% type 1 error rate). All analyses will be conducted on an intention-to-treat basis and will be conducted under the quality system and SOPs of the HRB CRF-C Statistics and Data Analysis Unit. A complete statistical analysis plan (SAP) will be pre-registered on the Open Science Framework prior to database lock. Any necessary deviations from this SAP will be documented and explained in the trial report. There will be only one single trial data analysis at the end of the project. All reporting will be carried out in accordance with CONSORT guidelines for clinical trials.

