2.2 Aims of the study

- (i) Primary aim: to determine if a medication optimization DI can significantly reduce all-cause re-hospitalization and unscheduled emergency department attendance at 30 days and between 90 and 180 days in multi-morbid older people exposed to polypharmacy. To achieve this, we will measure the following outcomes: Unscheduled readmission within 30 days and between 90 and 180 days post-discharge, ED attendance within 30 and between 90 and 180 days post-discharge, and a primary composite endpoint of unscheduled readmission or ED attendance within 30 and between 90 and 180 days post-discharge.
- (ii) Secondary aims:
 - (a) To determine the effects of the DI on secondary endpoints, including quality of life (EQ5D-5L), all-cause mortality and referral to nursing home for long-term care.
 - (b) To compare endpoints achieved through standard pharmaceutical care (control) with those achieved through physician-delivered DI and pharmacist-delivered DI. This is to determine if DI delivery by a trained pharmacist is more/less/equally effective compared to DI delivery by a trained physician.

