2.3 Research Question /Hypothesis

Hypothesis 1: A multi-faceted medication optimization definitive intervention (DI) based on explicit inappropriate prescribing criteria, potential prescribing omission criteria and drug-drug and drug-disease interaction surveillance applied following admission and pre-discharge from hospital in older people with multi-morbid illness and associate polypharmacy supplemented by structured follow-up with patients' GPs and community pharmacists as well with patients themselves results in significantly lower rates of unscheduled rehospitalization or emergency department attendance or both compared to standard current pharmaceutical care.

Hypothesis 2: The same multi-faceted medication optimization DI has an equal effect on rates of unscheduled rehospitalization or emergency department attendance or both when delivered by a trained pharmacist compared to a trained physician.

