4.3 Sampling and Randomization (if applicable)

To test the main study hypothesis i.e. that the definitive intervention (DI) yields significantly better outcomes than standard pharmaceutical care (control), patients will be randomized in a 1:1:1 ratio to one of 3 trial arms: (a) standard pharmaceutical care as it contemporaneously exists in that hospital, or (b) trained physician-delivered intervention or (c) clinical pharmacist-delivered intervention. The 3-way randomization to control, Physician-DI and Pharmacist DI is fundamental to addressing the important secondary question: does physician-delivered DI offer any advantage over pharmacist-delivered DI?

The sample size is based on a known 180-day risk of medication-related readmission of approximately 20%. At a bilateral 5% significance threshold and 80% power, for detection of an 8% absolute reduction in readmissions, with a 1:1:1 randomization, each group must contain 324 patients i.e. 972 patients in total. With the expectation of up to 30% patient attrition, we aim to randomize $972/(1-0.3) = 1389$ patients.

The randomization will be designed by the trial statistician, but the code to create the resulting randomization lists will be executed by an independent statistician. The resulting lists will be integrated into the electronic data capture system in a manner such that trial staff never have access to the lists. Allocation of enrolled patients into treatment arms will then be delivered using a web-based system, such that the allocation remains concealed until a patient is unambiguously consented and enrolled onto the trial and cannot be altered in the underlying database once it is revealed. While the intervention will be known to clinical staff, the trial statistician and outcome assessors will remain blinded until the results are finalized.

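### The physician–pharmacist equivalence conclusion is not tied to benefit over control, so two ineffective DI arms could be reported as equally effective

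*Combined protocol and SAP*

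**What the plan says.** Section 7.2 estimates each active arm against control for each outcome. It then compares the two active arms by TOST using a 90% confidence interval. It adds that "All analyses will be conducted on an intention-to-treat basis", rules out multiplicity correction and sets no order of testing. The Synopsis and Section 6.1 repeat the plan for equivalence tests on each outcome. No equivalence margin is given, and no analysis by delivery or uptake of the DI is named.

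Two sections say how the result will be read. Hypothesis 2 in Section 2.3 is that the DI "has an equal effect on rates of unscheduled rehospitalization or emergency department attendance or both when delivered by a trained pharmacist" as when delivered by a physician. The secondary aim in Section 2.2 is "to determine if DI delivery by a trained pharmacist is more/less/equally effective compared to DI delivery by a trained physician". Section 3.1 also lists the physician–pharmacist comparison among the primary objectives.

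The end of Section 2.1 says that the comparison bears on how the DI would be rolled out, provided that the DI is shown to be significantly better than usual pharmaceutical care. Section 7.2 does not carry that condition into the analysis.

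**The concern.** An equivalence test between two active arms shows only that their event rates are close. It cannot tell two arms that work equally well from two arms that work equally little. In the second case there is no effect to be equal, yet the test as planned passes, and Sections 2.2 and 2.3 supply the words equal effect and equally effective for that result.

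The protocol gives reasons to take a null DI seriously. Section 2.1 reports 15% implementation of software-generated advice in one earlier trial, and attributes two null trials largely to poor adherence with advice. Section 11.1 lets hospital doctors and GPs reject any advice point.

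At stake is the conclusion on which profession could deliver the DI. A statement that pharmacists and physicians are equally effective could be drawn from a trial in which neither improved on usual care.

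**Working it through.** **Inputs.** All design inputs come from Section 4.3: "At a bilateral 5% significance threshold and 80% power"; a "known 180-day risk of medication-related readmission of approximately 20" per cent; "for detection of an 8% absolute reduction in readmissions, with a 1:1:1 randomization"; "each group must contain 324 patients i.e. 972 patients in total"; and "With the expectation of up to 30% patient attrition, we aim to randomize" 1389. The equivalence test uses a 90% interval (Section 7.2). The margin M is not stated, so 5 to 10 percentage points on the absolute risk scale is assumed.

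**The plan's own figure.** For 20% versus 12%, the pooled formula gives n = [1.96·√(2·0.16·0.84) + 0.842·√(0.2·0.8 + 0.12·0.88)]² / 0.08² = 329 per arm. The unpooled version gives 326 and the arcsine version 325. The stated 324 is reproduced to within 1.5%, with power of 79.5%. Then 972/0.7 = 1389, or 463 per arm. The plan states no sample size or power for the equivalence test.

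**Pass rate when the DI does nothing (20% in every arm).**

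- SE = √(2·0.2·0.8/324) = 0.0314, so the 90% half-width is 1.645·0.0314 = 0.0517.
- P(pass) = 2Φ(M/SE − 1.645) − 1.
- At M = 0.08: 0.08/0.0314 = 2.546; 2.546 − 1.645 = 0.901; 2Φ(0.901) − 1 = 0.63.

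| Assumed margin | 324 per arm | 463 per arm |
|---|---|---|
| 5 points | about 1% | 20% |
| 6 points | 21% | 48% |
| 8 points | 63% | 84% |
| 10 points | 88% | 97% |

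The 5-point entry for 324 per arm is 0.6% by simulation. The formula gives zero because the half-width exceeds the margin. If the risk were 40% rather than 20%, the figures at 6, 8 and 10 points with 324 per arm would be 0%, 34% and 66%.

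**Effect of a rule tying equivalence to benefit over control.** This was simulated with 400,000 trials per scenario, 324 per arm, pooled z tests against control and an 8-point margin. The gated figure is the pass rate minus the share of trials that pass with neither arm superior to control.

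| True risks, control/DI/DI | No gate | Pass, neither arm superior | At least one arm superior | Both arms superior |
|---|---|---|---|---|
| 20/20/20 | 63.5% | 61.9% | 1.6% | 0.4% |
| 20/16/16 | 74.0% | 48.5% | 25.5% | 11.9% |
| 20/12/12 | 86.4% | 8.5% | 77.9% | 63.2% |

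At a 10-point margin, the at-least-one-arm rule takes the no-effect case from 87.6% to 87.6 − 84.6 = 3.0%, and the 20/12/12 case from 97.7% to 97.7 − 9.0 = 88.7%.

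**The case against.** Four points on the other side carry weight.

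- **The control arm is used.** A reader might infer that the plan ignores it. It does not: the Synopsis and Sections 6.1 and 7.2 compare each DI arm with control for every outcome, and Section 7.2 reports all outcomes whatever the result. Two failed arms would appear beside two null comparisons, and Section 2.1 already makes roll-out conditional on benefit. What remains is that the analysis section does not say how to read an equivalence pass when the DI has failed.
- **Intention-to-treat is a defensible primary set.** A reader might infer that incomplete delivery produces false equivalence verdicts. Suppose one arm's full-delivery effect is 8 points and the other's is zero, with effect proportional to delivery. Then 60% or 40% delivery gives true intention-to-treat differences of 0.6 × 8 = 4.8 and 0.4 × 8 = 3.2 points. Both lie inside an 8-point margin, so a pass is correct for the effect being estimated. Uptake is also part of the practical question: Section 2.1 reports STOPP/START implementation of 81.2%/87.4% with a physician and 39.2%/29.5% with a pharmacist in earlier studies.
- **The size depends on the missing margin.** At 5 points and 324 per arm the test rarely passes at all. The plan also reports odds ratios, while these margins are on the absolute scale. Stating a margin would fix the size of the risk, but would not by itself stop two failed arms from passing.
- **A full SAP is still to be registered before database lock.** The rule may appear there. It is not in the documents available.

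**Conclusion.** The point holds as a gap in interpretation. Nothing in Section 7.2 ties a conclusion of equal effectiveness to benefit over control. With 324 per arm and 20% risk throughout, an ineffective DI would pass about 21%, 63% or 88% of the time at assumed margins of 6, 8 or 10 points, and about 1% at 5 points. If all 463 randomized patients per arm were analysed, the risk would be larger at each of these margins.

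The figures rest on the protocol's 20% risk, an absolute-risk margin that the plan does not state, and a normal approximation or simulation without covariate adjustment. The documents do not support the stronger readings that the control arm goes unused or that intention-to-treat is the wrong primary set for this comparison.

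**What to change.** Add to Section 7.2, and carry into the registered SAP:

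1. Equivalence on an outcome is interpreted as equally effective only if at least one DI arm is superior to control on that outcome. Otherwise the report states that no DI effect was shown and that equivalence of effect is not assessable. The interval for the difference between the two DI arms is still reported.
2. Intention-to-treat remains the primary set. A pre-specified supportive equivalence analysis by DI delivery is added, preferably a complier-type estimate, using the components scheduled in Table 1a.

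The first change is wording only and uses comparisons already planned. At an 8-point margin, the chance of claiming equivalence falls from about 86% to 78% when both arms achieve the planned effect. The loss is larger if the effect is half that size (74% to about 26%), because superiority over control is then hard to show. Requiring both arms to be superior would cost more (63% under the planned effect) for little further protection.

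The supportive analysis should not be a second condition for equivalence. Restricting to patients who received the components selects after randomization. If 60% received them all (about 0.6 × 324 = 194 per arm) and both arms sat at 12%, TOST at 8 points would pass only about 56% of the time. Table 1a schedules the procedures but does not define receipt of the DI, so the sponsor would need to define it and confirm that it is recorded per patient. The equivalence margin must be stated in any case.
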